11.9.5. Efficacy Figures

Efficacy Figures					
No.	Population	IDSL / TST ID / Example Shell	Title	Programming Notes	Deliverable
Serum Creatinine					
2.01	All Subjects	Non-Standard EFF_F1	Individual Line Plot of Serum Creatinine over Time	Including the mean line plot; starting from baseline	IA1, IA2, SAC
2.02	All Subjects	Non-Standard EFF_F1	Individual Line Plot of Serum Creatinine Change from Baseline over Time	Including the mean line plot	IA1, IA2, SAC
Graft function					
2.03	All Subjects	Non-Standard EFF_F2	Individual Line Plot of Urine Output over Time		IA2, SAC
2.04	All Subjects	Non-Standard EFF_F3	Kaplan-Meier Curve of Graft Survival up to 12 Months post Transplant		IA2, SAC
PD biomarkers					
2.05	All Subjects	Non-Standard EFF_F1	Individual Line Plot of Serum IP-10 over Time	Including the mean line plot; starting from baseline	IA2, SAC
2.06	All Subjects	Non-Standard EFF_F1	Individual Line Plot of Serum IP-10 Change from Baseline over Time	Including the mean line plot	IA2, SAC
2.07	All Subjects	Non-Standard EFF_F1	Individual Line Plot of Serum Mig over Time	Including the mean line plot; starting from baseline	IA2, SAC

Efficacy Figures					
No.	Population	IDSL / TST ID / Example Shell	Title	Programming Notes	Deliverable
2.08	All Subjects	Non-Standard EFF_F1	Individual Line Plot of Serum Mig Change from Baseline over Time	Including the mean line plot	IA2, SAC
2.09	All Subjects	Non-Standard EFF_F1	Individual Line Plot of Serum IL-18 Levels over Time	Including free IL-18; bound IL-18 and total IL-18 Including the mean line plot	IA1, IA2, SAC
2.10	All Subjects	Non-Standard EFF_F1	Individual Line Plot of Serum IL-18 Levels Change from Baseline over Time	Including free IL-18; bound IL-18 and total IL-18 Including the mean line plot	IA2, SAC
Urine Biomarkers					
2.11	All Subjects	Non-Standard EFF_F3	Mean (95% CI) Plot of Urine IL-18	Two sided confidence interval	IA2, SAC
2.12	All Subjects	Non-Standard EFF_F3	Mean (95% CI) Plot of Urine NGAL	Two sided confidence interval	IA2, SAC
2.13	All Subjects	Non-Standard EFF_F3	Mean (95% CI) Plot of Urine KIM1	Two sided confidence interval	IA2, SAC
Exploratory					
2.14	All Subjects	Non-Standard EFF_F2	Individual Line Plot of Serum IL-18 Binding Protein over Time	starting from baseline	IA2, SAC
2.15	All Subjects	Non-Standard EFF_F2	Individual Line Plot of Serum Cytokine Levels over Time	starting from baseline	IA2, SAC

Efficacy Figures					
No.	Population	IDSL / TST ID / Example Shell	Title	Programming Notes	Deliverable
2.16	All Subjects	Non-Standard EFF_F1	Individual Line Plot of Serum Cytokine Levels Change from Baseline over Time	Including the mean line plot	IA2, SAC
Patient Profile					
2.17	All Subjects	Non-Standard EFF_F5	Patient Profile Plot of Biomarker/PD Endpoints	Including serum IP-10; serum mig; free IL-18; bound IL-18; total IL-18	IA2, SAC

11.9.6. Safety Tables

Safety Tables					
No.	Population	IDSL / TST ID / Example Shell	Title	Programming Notes	Deliverable
Adverse Events – Overall					
3.01	All Subjects	AE1	Summary of All Adverse Events		IA1, IA2, SAC
3.02	All Subjects	AE3	Summary of Common Adverse Events by Preferred Term	Common AE = Frequency > 1%	IA1, IA2, SAC
3.03	All Subjects	AE1	Summary of Drug-Related Adverse Events by System Organ Class		IA1, IA2, SAC
3.04	All Subjects	AE1	Summary of Serious Adverse Events by System Organ Class		IA1, IA2, SAC
3.05	All Subjects	AE1	Summary of Adverse Events Leading to Withdrawals from Study or Study Treatment		IA1, IA2, SAC
Adverse Events – in patients (before discharge)					
3.06	All Subjects	AE1	Summary of All Adverse Events before Discharge		IA2, SAC
3.07	All Subjects	AE3	Summary of Common Adverse Events by Overall Frequency before Discharge		IA2, SAC
3.08	All Subjects	AE5	Summary of Drug-Related Adverse Events by System Organ Class before Discharge		IA2, SAC

Safety Tables					
No.	Population	IDSL / TST ID / Example Shell	Title	Programming Notes	Deliverable
3.09	All Subjects	AE1	Summary of Serious Adverse Events by System Organ Class before Discharge		IA2, SAC
3.10	All Subjects	AE1	Summary of Adverse Events Leading to Withdrawals from Study / Permanent Discontinuation of Study Treatment before Discharge		IA2, SAC
Adverse Events – out patients (after discharge)					
3.11	All Subjects	AE1	Summary of All Adverse Events after Discharge		IA2, SAC
3.12	All Subjects	AE3	Summary of Common Adverse Events by Overall Frequency after Discharge		IA2, SAC
3.13	All Subjects	AE5	Summary of Drug-Related Adverse Events by System Organ Class after Discharge		IA2, SAC
3.14	All Subjects	AE1	Summary of Serious Adverse Events by System Organ Class after Discharge		IA2, SAC
3.15	All Subjects	AE1	Summary of Adverse Events Leading to Withdrawals from Study / Permanent Discontinuation of Study Treatment after Discharge		IA2, SAC
Labs					
3.16	All Subjects	LB1	Summary of Chemistry Changes from Baseline		IA2, SAC

Safety Tables					
No.	Population	IDSL / TST ID / Example Shell	Title	Programming Notes	Deliverable
3.17	All Subjects	LB1	Summary of Emergent Chemistry Results of Potential Clinical Importance		IA1, IA2, SAC
3.18	All Subjects	LB1	Summary of Haematology Changes from Baseline		IA2, SAC
3.19	All Subjects	LB1	Summary of Emergent Haematology of Potential Clinical Importance		IA1, IA2, SAC
Vital Signs					
3.20	All Subjects	VS1	Summary of Change from Baseline in Vital Signs	Include the Respiration Rate and Temperature	IA2, SAC
3.21	All Subjects	VS2	Summary of Emergent Vital Signs Results of Potential Clinical Importance		IA1, IA2, SAC
ECGs					
3.22	All Subjects	EG1	Summary of ECG Findings		IA2, SAC
3.23	All Subjects	Non-Standard EFF_T5	Frequency of Maximum Emergent QTc Values by Category		IA1, IA2, SAC
3.24	All Subjects	EG2	Summary of Change from Baseline in ECG Values		IA2, SAC

11.9.7. Pharmacokinetic Tables

Pharmacokinetic Tables					
No.	Population	IDSL / TST ID / Example Shell	Title	Programming Notes	Deliverable
PK Concentration Data					
4.01	PK	PK01	Summary of Plasma GSK1070806 Pharmacokinetic Concentration-Time Data (mg/mL)		IA1, IA2, SAC
PK Derived Parameters					
4.02	PK	PKPT1	Summary Statistics of Derived Plasma GSK1070806 Pharmacokinetic Parameters	Parameters with units	IA1, IA2, SAC
4.03	PK	PKPT3	Summary Statistics of Log-Transformed Derived Plasma GSK1070806 Pharmacokinetic Parameters	Parameters with units; exclude non-continuous PK parameters;	IA2, SAC

11.9.8. Pharmacokinetic Figures

Pharmacokinetic Figures					
No.	Population	IDSL / TST ID / Example Shell	Title	Programming Notes	Deliverable
Individual Plots					
4.01	PK	PKCF1P	Individual GSK1070806 Plasma Concentration-Time Plot by Subject (Linear and Semi-Log)	Paginate by Subject	IA2, SAC
Mean / Median Plots					
4.02	PK	PKCF2	Mean and Median Plasma GSK1070806 Concentration-Time Plots by Treatment (Linear and Semi-log)		IA2, SAC
4.03	PK	PKCF3	Median and Median Plasma GSK1070806 Concentration-Time Plots by Treatment (Linear and Semi-log)		IA2, SAC

11.9.9. Pharmacokinetic / Pharmacodynamic Figures

Pharmacodynamic / Biomarker Figures					
No.	Population	IDSL / TST ID / Example Shell	Title	Programming Notes	Deliverable
5.01	PK	Non-Standard PKPD_F1	Scatter Plot of Free and Drug Bound IL-18 Serum Levels Versus GSK1070806 Plasma Concentration	Panel : by free and drug bound IL-18 X-Axis : Plasma Concentration Y-Axis : free and drug bound IL-18 Add Footnote X-Axis: Untransformed data presented using Log10 scale	IA2, SAC

11.9.10. ICH Listings

ICH Listings					
No.	Population	IDSL / TST ID / Example Shell	Title	Programming Notes	Deliverable
Subject Disposition					
1	All Subjects	ES2	Listing of Reasons for Study Withdrawal		IA1, IA2, SAC
2	All Subjects	ES7	Listing of Reasons for Screening Failure		IA1, IA2, SAC
3	All Subjects	SA3a	Listing of Subjects Excluded from Any Populations		IA2, SAC
4	All Subjects	DV2	Listing of Important Protocol Deviations		IA1, IA2, SAC
5	All Subjects	IE3	Listing of Subjects with Inclusion/Exclusion Criteria Deviations		IA1, IA2, SAC
Demographics					
6	All Subjects	DM2	Listing of Demographic Characteristics		IA1, IA2, SAC
7	All Subjects	DM9	Listing of Race		IA1, IA2, SAC
Exposure					

ICH Listings					
No.	Population	IDSL / TST ID / Example Shell	Title	Programming Notes	Deliverable
8	All Subjects	EX3	Listing of Exposure		SAC
Adverse Events					
9	All Subjects	AE7	Listings of Subject Numbers for Individual Adverse Events		IA1, IA2, SAC
10	All Subjects	AE8	Listing of All Adverse Events		IA1, IA2, SAC
11	All Subjects	AE8	Listing of Serious Adverse Events		IA1, IA2, SAC
12	All Subjects	AE8	Listing of Adverse Events Leading to Withdrawal from Study		IA1, IA2, SAC
LABS					
13	All Subjects	LB5	Listing of Haematology Laboratory Data for Subjects with Abnormalities of Potential Clinical Importance		IA1, IA2, SAC
14	All Subjects	LB5	Listing of Clinical Chemistry Laboratory Data for Subjects Abnormalities of Potential Clinical Importance.		IA1, IA2, SAC
15	All Subjects	UR2b	Listing of Urinalysis Data		IA2, SAC

CONFIDENTIAL

204824

ICH Listings					
No.	Population	IDSL / TST ID / Example Shell	Title	Programming Notes	Deliverable
16	All Subjects	Non-Standard SAFE_L1	Listing of Clinical Chemistry Laboratory Values (Total cholesterol, HDL, LDL, Triglycerides, Creatinine Clearance (MDRD) and Associated Ratios).		IA2, SAC
ECGs					
17	All Subjects	EG3	Listing of ECG Values for Subjects with Abnormalities of Potential Clinical Importance.		IA1, IA2, SAC
Vital Signs					
18	All Subjects	CP_VS4	Listing of Vital Signs for Subjects with Abnormalities of Potential Clinical Importance		IA1, IA2, SAC
Immunogenicity					
19	All Subjects	IMM2	Listing of Immunogenicity Results	ADA tiers	IA2, SAC

11.9.11. Non-ICH Listings

Non-ICH Listings					
No.	Population	IDSL / TST ID / Example Shell	Title	Programming Notes	Deliverable
PK					
20	PK	PKCL1P	Listing of Plasma GSK1070806 Pharmacokinetic Concentration-Time Data		IA2, SAC
21	PK	PKPL1P	Listing of Derived Plasma GSK1070806 Pharmacokinetic Parameters	Include dose and dose number	IA2, SAC
Graft Function					
22	Analysis Population	Non-Standard SAFE_L1	Listing of Individual Serum Creatinine		IA1, IA2, SAC
23	Analysis Population	Non-Standard SAFE_L1	Listing of Individual AUC of 7 Day Serum Creatinine	No change from baseline column	IA1, IA2, SAC
24	Analysis Population	Non-Standard SAFE_L1	Listing of Individual AUC of 30 Day Serum Creatinine	No change from baseline column	IA1, IA2, SAC
25	All Subjects	Non-Standard SAFE_L2	Listing of Individual Graft Function in the First 7 Days	Including primary non function;3 day functional DGF; 7 day functional DGF; 3 day intermediate graft function; 7 day intermediate graft function; 3 day immediate graft function; 7 day immediate graft function	IA1, IA2, SAC

Non-ICH Listings					
No.	Population	IDSL / TST ID / Example Shell	Title	Programming Notes	Deliverable
26	All Subjects	Non-Standard SAFE_L2	Listing of Individual Urine Output	Including change from baseline	IA2, SAC
27	All Subjects	Non-Standard SAFE_L1	Listing of Individual with Episodes of Biopsy-Proven Acute Rejection		IA2, SAC
Pharmacodynamic & Biomarkers					
28	All Subjects	Non-Standard EFF_L1	Listing of Individual of IL-18		IA1, IA2, SAC
29	All Subjects	Non-Standard EFF_L1	Listing of Individual of NGAL		IA2, SAC
30	All Subjects	Non-Standard EFF_L1	Listing of Individual of KIM1		IA2, SAC
31	All Subjects	Non-Standard PD_L1	Listing of Biomarkers		IA2, SAC
32	All Subjects	Non-Standard PD_L1	Listing of Free and Drug-bound IL-18 Levels In Serum		IA2, SAC
Dialysis dependency and graft survival					
33	All Subjects	Non-Standard SAFE_L1	Listing of Number of Dialysis Events per Patient in the First 30 Days Post Transplant		IA1, IA2, SAC

Non-ICH Listings					
No.	Population	IDSL / TST ID / Example Shell	Title	Programming Notes	Deliverable
Recipient Kidney Data					
34	All Subjects	Non-Standard SAFE_L3	Listing of Recipient Virology		IA2, SAC
Exploratory					
35	All Subjects	Non-Standard SAFE_L1	Listing of Individual % bound GSK1070806 within Renal Graft Biopsies		IA2, SAC
36	All Subjects	Non-Standard SAFE_L1	Listing of Individual Level of IL-18 in Renal Preservation Fluid		IA2, SAC
37	All Subjects	Non-Standard SAFE_L1	Listing of Individual Change from Baseline Histological Analysis of Biopsies with Respect to Cellular Infiltrate		IA2, SAC
38	All Subjects	Non-Standard SAFE_L2	Listing of Individual of Length of Hospital and Re-hospitalization Stay		IA1, IA2, SAC
Donor Kidney Data					
39	All Subjects	Non-Standard SAFE_L3	Listing of Donor Virology		IA2, SAC
40	All Subjects	Non-Standard SAFE_L4	Listing of Donor Characteristics	Cold ischemic time; warm ischemic time; age; sex; last creatinine before transplant; medical conditions; biopsy performed yes/no, transport system (ice or perfusion)	IA1, IA2, SAC

CONFIDENTIAL

204824

[figure not shown]
Non-ICH Listings					
No.	Population	IDSL / TST ID / Example Shell	Title	Programming Notes	Deliverable
PK/PD					
41	PK	Non-Standard SAFE_L5	Listing of Serum IL-18 (drug bound, total or free) vs. PK Plasma Concentrations		IA2, SAC

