
 To determine immunogenicity of GSK1070806 in renal transplant recipients. 	
 Frequency of anti-drug antibodies (ADAs) before and after GSK1070806 administration. ADA titers.

Objectives	Endpoints
Exploratory	Exploratory

 To assess the impact of GSK1070806 on urine biomarkers of renal injury. 	
 Serial measurements of urinary biomarkers, including KIM-1, NGAL and IL-18, at baseline and over time post transplant.

 To assess IL-18 target engagement in the kidney. 	
 GSK1070806 and IL-18 levels within renal graft biopsies, as assessed by immunohistochemistry.

 To assess the relation between IL-18 levels in renal preservation fluid and graft function. 	
 Level of IL-18 in renal preservation fluid.

 To assess the impact of GSK1070806 administration on IL-18 binding protein levels. 	
 Serum IL-18 binding protein at baseline and over time post transplant.

 To assess the humoral and cellular response to the transplanted organ in the presence of GSK1070806. 	
 Serum cytokine levels at baseline and over time post transplant. Histological analysis of biopsies with respect to cellular infiltrate.

 To assess health outcomes in renal transplant recipients following GSK1070806 administration. 	
 Length of hospital stay Re-hospitalization

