11.2. Appendix 2: Time and Events

Study Day ¹	Screening	Pre-operative (baseline)	Intra-operative (D0) ¹	4-8h ²	D1	D2	Daily until discharge	Discharge	D30	D90	6 & 12 months ¹³	Unscheduled Visit
Informed Consent/Demographics	X											
Medical/drug/alcohol/tobacco history	X											
GSK1070806 IV Infusion			←-----→ ¹⁵									
Kidney preservation fluid IL-18			X ¹⁶									
Kidney biopsy (post-reperfusion) ³			X (~45 min)									
Clinical biopsy reports (if applicable)			←-----→									
Concomitant medication	X	X	X ¹⁷	X	X	X	X	X	X	X	X	X
Evidence of infection	X			X	X	X	X	X	X	X	X	X
SAE / AE monitoring			←-----→									
DGF status (up to day 7)				←-----→								
Urine output		X (native output)	X	X	X	X	X					
Dialysis events since last assessment		X		X	X	X	X	X	X	X	X	X
Graft survival			←-----→									
Viral serology (recipient & donor – HIV, Hep B/C, EBV) ⁴	X ⁵	X									X	X
Viral serology (recipient & donor -herpes, varicella) ⁴		X										
CMV monitoring	X ⁵	X									X	X
BK virus monitoring ⁶		X							X	X	X	X
Vital signs ⁷	X			X	X	X	X	X	X	X	X	X
Complete physical	X										X	X
12-lead ECG	X							X			X	X
Hematology / Clinical Chemistry / Urinalysis	X			X	X	X	X	X	X	X	X	X
Pregnancy test ⁸	X								X	X	X	X
Serum cytokines / PD biomarkers		X ¹¹	X (~45 min at biopsy)	X	X	X		X	X	X	X	X

Study Day ¹	Screening	Pre-operative (baseline)	Intra-operative (D0) ¹	4-8h ²	D1	D2	Daily until discharge	Discharge	D30	D90	6 & 12 months ¹³	Unscheduled Visit
Free, GSK1070806 bound & total IL18 ⁹		X ¹¹	X (~45 min at biopsy)	X	X	X		X	X	X	X	X
Pharmacokinetics ^{9,10}		X ¹¹	X (~45 min at biopsy)	X	X			X (@168 hrs or at earlier discharge)	X	X	X	X
Immunogenicity ¹²		X ¹¹							X	X	X	X
Urinary biomarkers		X ¹¹		X	X	X	X	X	X	X	X	X
Peripheral blood leucocyte flow phenotyping ¹⁴		X						X		X	X	
PBMCs frozen for in vitro stimulation assays ¹⁴		X						X		X	X	
PBMCs placed in trizol for transcriptomic analysis ¹⁴		X						X		X	X	

1. Day 0 defined as the calendar day of transplant.
2. Time post reperfusion.
3. Biopsies during transplantation may be 'core or wedge' at the discretion of the operating surgeon. If, in the judgement of the operating surgeon, biopsy poses unwarranted risk to the patient, it may be omitted.

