11.4. Appendix 4: Data Display Standards & Handling Conventions

11.4.1. Baseline Definition & Derivations

11.4.1.1. Baseline Definitions

For all endpoints baseline value will be the latest pre-dose assessment.

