11.4.1.2. Derivations and Handling of Missing Baseline Data

Definition	Reporting Details
Change from Baseline	= Post-Baseline Visit Value – Baseline
[% Change from Baseline]	= [(Post-Baseline Visit Value – Baseline) / Baseline] x 100]

NOTE :

- Unless otherwise specified, the baseline definitions specified in [11.4.1.1Baseline Definitions](#) will be used for derivations for endpoints / parameters and indicated on summaries and listings.
- Unless otherwise stated, if baseline data is missing no derivation will be performed and will be set to missing.
- The baseline definition will be footnoted on all change from baseline displays.

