11.6.2.3. Handling of Missing Data for Statistical Analysis/Efficacy Endpoints

Element	Reporting Detail
All Endpoints	
• Missing values will not be imputed.

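### The cellular-infiltrate endpoint is planned only as a change from baseline, but no pre-dose biopsy is scheduled, so that change is missing for every subject on scheduled data

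*SAP*

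**What the plan says.** Section 2.2 states the exploratory objective as "To assess the humoral and cellular response to the transplanted organ in the presence of GSK1070806". It gives two endpoints: serum cytokine levels at baseline and over time, and "Histological analysis of biopsies with respect to cellular infiltrate". The histology endpoint is not worded as a change.

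Section 8.1.1, Table 3, marks the histology endpoint once, in the last column: change from baseline, individual, listing. No absolute table, figure or listing is marked. Section 11.9.11 has one display for it, Listing 37, "Listing of Individual Change from Baseline Histological Analysis of Biopsies with Respect to Cellular Infiltrate", on shell SAFE_L1, for the second interim and the final analysis.

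Section 11.4.1.1 defines baseline without exception: "For all endpoints baseline value will be the latest pre-dose assessment". Section 11.4.1.2 adds that, unless otherwise stated, "if baseline data is missing no derivation will be performed and will be set to missing". Section 11.6.2.3 says of all endpoints: "Missing values will not be imputed".

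In Appendix 2 (Section 11.2), the row that begins "Kidney biopsy (post-reperfusion" has one mark, intra-operative on Day 0 at about 45 minutes. Footnote 3 lets the surgeon omit this biopsy. Footnote 15 requires the infusion to end before reperfusion. A second row, beginning "Clinical biopsy reports (if applicable", collects reports of clinical biopsies from the operation onward.

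**The concern.** A change from baseline needs a pre-dose value and a later one. The schedule supplies no pre-dose biopsy, and the SAP names no substitute reference for histology. If the plan is followed literally, the quantity in the title of Listing 37 does not exist for anyone, and the listing must carry a footnote to a baseline that no scheduled assessment provides.

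At stake is whether this endpoint is reported in a usable form. If the mismatch is noticed only during programming, someone will have to choose a reference biopsy, and decide whether clinical biopsies count, after results are available.

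**Working it through.** The SAP states no figure to reproduce. The check sets its provisions side by side.

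**1. Is the endpoint really planned only as a change?** Tables can be damaged in text extraction, so the position of a single mark in Table 3 is weak evidence alone. The title of Listing 37 says the same independently, and no other display covers infiltrate. Listing 27 covers biopsy-proven rejection, which is a different endpoint. So yes.

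**2. Is the scheduled biopsy pre-dose?** Under footnote 15 the infusion is over before reperfusion, and the biopsy comes about 45 minutes after reperfusion, so it is post-dose. Footnote 10 instead ties the biopsy to a sample taken 45 minutes to 1 hour into the infusion. The two footnotes conflict and must be reconciled, but under neither does the biopsy precede the start of dosing.

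**3. What do the derivation rules then give?**

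| Quantity | Per subject | Up to 30 subjects |
|---|---|---|
| Scheduled pre-dose biopsies | 0 | 0 × 30 = 0 |
| Changes derivable (Sections 11.4.1.1 and 11.4.1.2) | 0 | 0 × 30 = 0 |
| Scheduled post-dose biopsies | at most 1 | at most 1 × 30 = 30 |

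The planned change is therefore missing for 30 of 30, or 100%, at the maximum sample size, and for 100% at any smaller one. Clinical biopsies collected after transplantation do not alter this, since they too are post-dose.

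**4. What survives without the change?** Shell SAFE_L1 in Appendix 10 has a Result column beside the change column, and its note allows the layout to be adapted to the data. Section 11.4.2 says that all unscheduled visits are listed. Raw findings from the 45-minute biopsy, and possibly from later clinical biopsies, can therefore appear. No provision says whether clinical reports feed Listing 37.

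**5. Does the SAP treat its other biopsy endpoints this way?** No. Table 3 plans the free and bound percentages of GSK1070806 in graft biopsies as absolute table and listing, with no change. Listings 23 and 24 carry a programming note that removes the change column. Listing 37 has no such note. A related slip runs the other way: Tables 2.25 to 2.27, which Table 3 treats as absolute, are assigned the change-from-baseline shell EFF_T2.

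**The case against.** The strongest reply is that this is a labelling slip in one exploratory listing. The endpoint does not require a change, the shell shows the raw result, and a programmer would list what exists and leave one column blank. That stands as a limit on importance. It does not remove the contradiction, because the title and Table 3 both ask for a quantity that the SAP's own rules make underivable.

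Three stronger readings are tempting and are not supported:

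- *The endpoint has no computable value.* Only the change is lost; the observed finding is not.
- *The cellular-response objective goes unanswered, or a later response cannot be seen.* Serum cytokines serve the same objective, with samples scheduled before infusion, and appear in Table 2.28 and Figures 2.15 and 2.16. Clinical biopsy reports are collected and could show later infiltration in the subjects who have them. Whether 45 minutes is too early for the scheduled biopsy is a question for the protocol, not an error in this SAP.
- *No pre-dose tissue exists.* The SAP shows only that none is scheduled. Listing 40 records whether a donor biopsy was performed, and nothing says whether one could serve as a reference.

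It is also fair to resist making the 45-minute biopsy a new baseline. That biopsy is post-dose and optional, the later ones are clinically indicated, and the SAP does not say that clinical reports grade infiltrate comparably. A change built on these would describe a selected subset.

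**Conclusion.** The point holds as an internal contradiction. The only planned form of the cellular-infiltrate endpoint is a change from a pre-dose baseline, and the schedule provides no such baseline, so 0 of up to 30 subjects have a derivable change on scheduled data.

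This rests on two readings: that Table 3 and the title of Listing 37 mean what they say, and that no histology-specific baseline is defined elsewhere in the SAP. None was found. The number of subjects with a later clinical biopsy is not given, so how much later histology could be listed cannot be sized.

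The consequence is confined to one exploratory listing. No primary, secondary or safety result depends on it.

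**What to change.** Before database freeze:

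1. In Table 3, move the mark for this endpoint to absolute, individual, listing.
2. Retitle Listing 37 as the observed cellular-infiltrate result, with the same programming note as Listings 23 and 24 so that the change column is dropped.
3. State that every available biopsy is listed, with time since reperfusion and type: scheduled at about 45 minutes, or clinically indicated.
4. Footnote that later biopsies were clinically indicated and so come from a selected subset of subjects.
5. Reconcile footnotes 10 and 15 of Appendix 2 on the timing of the biopsy relative to the infusion.

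A change from the 45-minute biopsy is optional. If shown, it should be labelled descriptive, with that biopsy named as the reference.

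The cost is a few lines of SAP text and an adjusted shell, with no extra biopsy or data collection. The listing would then make no within-subject change claim, which the scheduled data could not support anyway.
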